#### **3.3.12.3 Aim 2 (To evaluate the effect of psilocybin treatment on drinking outcomes for 32 weeks after the first administration, relative to diphenhydramine control)**

##### **3.3.12.3.1 Outcome measures**

The primary drinking outcome for hypothesis 2 is percent heavy drinking days during weeks 5-36 (the 32 weeks following the first drug administration session) as assessed by the Time-line Follow-back [100]. Other drinking variables will serve as secondary outcomes, including percent days abstinent, drinks per

drinking day, days to first drinking day, days to first heavy drinking day, and consequences of drinking (from the Short Inventory of Problems [101]).

### 3.3.12.3.2 Method

For PHDD we will employ a MMRM including fixed, categorical effects of treatment, assessment, and site; site-by-treatment and treatment-by-assessment interactions; the continuous, a fixed covariate (week 1-4 PHDD); and using monthly values of PHDD (weeks 5-8, 9-12, 13-16, 17-20, 21-24, 25-28, 29-32, 32-36) as the dependent measure. Site and the site-by-treatment interaction will be removed from the final model if not significant at the  $p < 0.05$  level. Secondary drinking measures with a continuous scale of measurement, i.e., PDA and DPDD, will be tested in a similar fashion and for days to first drinking day and days to first heavy drinking day (5 or more standard drinks for a man, 4 or more standard drinks for a woman). Cox survival analysis will be used. Measures of effect size will be calculated for all planned between-group contrasts (Hedges  $d$ ) and the  $Q$  statistic will be calculated to assess the homogeneity of effect across the primary and secondary outcome measures of drinking.

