#### **3.3.12.1 Preliminary analyses**

In addition to the assessment of the distributional properties of key measures at baseline and follow-up, we will evaluate the nature and pattern of missing data and assess treatment group equivalency at baseline on primary substance use measures and patient characteristics that are central to study aims.

*Self-selection and Attrition.* Baseline measures of substance use and other relevant characteristics will be used to compare eligible prospects who do and do not drop out prior to randomization and receiving study medication. Contingent on the scale of measurement of the comparison variable, unprotected t-tests and Chi Squares will be done to compare these groups. Two strategies will be used to examine the impact of post-randomization attrition on study internal validity, and both strategies will employ hierarchical linear modeling (HLM) with binary outcomes depicting attrition status (yes/no) jointly at post-medication session visits (Bernoulli function). First, we will examine attrition by group assignment. Here, the HLM will identify both the main effect of group assignment on later attrition as well as the potential for a group-by-time attrition effect. Second, group equivalency on factors potentially predictive of future drinking will be evaluated with t-tests using baseline drinking intensity and other characteristics as dependent measures.

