#### **3.3.12.7 Statistical power**

Power analysis is based on the primary outcome analysis contrasting the psilocybin group with the control group with respect to percent heavy drinking days in months 1-8 post pharmacologic treatment (Aim 2). With a total sample size of  $n = 180$  (90 assigned to psilocybin and 90 to control), and 5% attrition (realistic because useable data require only 1 month follow-up in participants who have already participated for 1 month,  $N = 171$ ) our power analysis was based on the assumption that four predictors would be in the regression-based HLM model. We estimate that the study has power of 0.8 to detect an effect of size  $f^2 = .065$ , with alpha = 0.05 (2-tailed) and no correction for multiple comparisons. This effect is comparable to that of naltrexone [9, 158, 159], and smaller than those observed in some recent trials of other promising medications [160-162]. Regardless of the statistical significance of these changes, standardized and non-standardized effect sizes will be computed for primary and secondary outcome variables. The addition of an open-label optional third dosing does not affect the required sample size for Aim 2 (primary outcome), but approximately doubles the sample size for Aim 1 and allows for the addition of Aim 5.

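### The primary heavy-drinking model gives each month its own treatment effect but one shared baseline slope; a baseline-by-month term is a nearly free safeguard against a small loss of precision and a conditional bias

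*Combined protocol and SAP*

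**What the plan says.** Section 3.3.12.3.1 sets the primary outcome as "percent heavy drinking days during weeks 5-36". Section 3.3.12.3.2 analyses it with an MMRM "using monthly values of PHDD (weeks 5-8, 9-12, 13-16, 17-20, 21-24, 25-28, 29-32, 32-36) as the dependent measure". The listed terms are treatment, assessment and site; the "site-by-treatment and treatment-by-assessment interactions"; and "the continuous, a fixed covariate (week 1-4 PHDD". No interaction between that covariate and assessment is listed, and the covariance structure is not stated. Percent days abstinent (PDA) and drinks per drinking day (DPDD) are to be modelled in a similar way.

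On missing data, section 3.3.12.7 starts from "90 assigned to psilocybin and 90 to control" and reaches N = 171 by allowing for "5% attrition (realistic because useable data require only 1 month follow-up". Section 3.3.12.1 plans to test attrition for an arm effect and for "the potential for a group-by-time attrition effect", and to compare the arms on baseline drinking. Neither result is tied to a change in the primary model.

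Section 3.3.12 sends the reader to a separate SAP for the full analysis description. That text was not in the material reviewed.

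**The concern.** Weeks 1-4 adjoin the first outcome month, while the last outcome month ends at week 36, after two dosing sessions and further therapy. Nothing in the documents gives a reason to expect weeks 1-4 drinking to predict month 8 with the same slope as month 1, though no month-specific figure is given either.

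Two things are at stake if the slope does change. With complete data, the shared slope adjusts most months imperfectly and costs some precision, but randomization keeps the contrast unbiased. With incomplete data, the model predicts the missing late months of a dropout from the wrong slope. If the slope declines and a heavier drinker leaves, the prediction is too high. If that happens more in one arm, the errors do not cancel. Should heavier-drinking controls leave more often, the error would favor psilocybin on the primary outcome.

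**Working it through.** **Model.** As listed (site terms aside), with X the weeks 1-4 PHDD, T the arm and j = 1 to 8:

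- Listed: Y_ij = μ_j + τ_j·T_i + β·X_i + e_ij
- With the interaction: Y_ij = μ_j + τ_j·T_i + β_j·X_i + e_ij

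The primary contrast is taken as the mean of the eight τ_j. Eight slopes instead of one adds 8 − 1 = 7 parameters.

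**What the plan's figures cover.** The allowance reproduces: 180 × 0.95 = 171. It counts people without one month of data, so it does not bound later loss. Table 1 schedules the Time-line Follow-back (TLFB) inside the outcome window at weeks 8, 12, 24 and 36. Months 3-5 therefore rest on the week 24 visit and months 6-8 on week 36: six of eight months on two visits. The stated power of 0.80 contains no baseline slope and cannot size this point. (As a separate matter, noncentral F power at N = 171 and f² = .065 is 0.754 with 4 numerator df and 0.798 with 3.)

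**Inputs not in the documents (assumed).** Month-specific slopes, PHDD SD, within-person correlation and dropout by week 36.

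**Simulation A: trial-sized.** 2,000 trials per scenario; 180 randomized; eight months; unstructured covariance by maximum likelihood; outcome SD 1; residual correlation 0.5 + 0.5·0.7^lag; true effect 0. Dropout depended on baseline drinking.

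Precision without dropout, as SD of the 8-month contrast:

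| True slope, month 1 to 8 | One slope | Month-specific | Variance ratio |
|---|---|---|---|
| constant 0.5 | 0.1119 | 0.1120 | about 1.00 |
| 0.7 to 0.3 | 0.1118 | 0.1103 | (0.1118/0.1103)² = 1.03 |
| 0.8 to 0.1 | 0.1209 | 0.1106 | (0.1209/0.1106)² = 1.20 |

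A separate complete-data calculation let the baseline-outcome correlation fall from 0.70-0.85 at month 1 to 0.33-0.57 at month 8. Over seven patterns the variance ratio was 1.010-1.040, worth 171 × 0.010 = 1.7 to 171 × 0.040 = 6.8 participants.

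Bias of the one-slope contrast is its mean minus that of the month-specific fit on the same data. For example, −0.0269 − (−0.0048) = −0.022. Negative favors psilocybin.

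| Dropout by week 36 | Slope 0.7 to 0.3 | Slope 0.8 to 0.1 | Type I error, one slope |
|---|---|---|---|
| about 6%, same relation to baseline in both arms | 0.001 or less in size | 0.001 or less in size | 5.1% / 6.1% |
| about 6%, heavier drinkers leave control only | −0.007 | −0.011 | 5.3% / 6.0% |
| about 6%, opposite selection in the two arms | −0.011 | −0.018 | 5.3% / 6.0% |
| 20%, control only | −0.022 | −0.038 | 6.1% / 7.2% |
| 20%, opposite | −0.039 | −0.066 | 7.6% / 10.1% |
| 33%, opposite | −0.068 | −0.117 | 10.6% / 18.4% |

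The Monte Carlo error of a rejection rate is about √(0.05 × 0.95/2000) = 0.5 percentage points. In the steep-decline case the one-slope rate was already 5.8% without dropout, so its rates should be read against that. Month-specific slopes gave 4.7-5.4% in every declining-slope scenario. With a constant true slope there was no bias at any dropout level.

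**Simulation B: large-sample** (n = 60,000; effect about 0.40 SD). All control dropouts came from the heaviest third and psilocybin dropouts were random, after months 1-3. The effect was overstated by 3-4% at 10% v 5% dropout and by 8-10% at 20% v 10% (0.40 × 0.08 to 0.10 = 0.032-0.040 SD). Equal 15% dropout in both arms gave no difference between models.

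**Simulation C: milder selection** (n = 12,000; effect 0.40 SD). Dropout fell after month 1, 2 or 5, as the TLFB visits imply. Control dropout was graded, at about 1.5 times the weight per baseline SD. Overstatement was 0.5-1.2% at 10% v 5% and 1.4-2.3% at 20% v 10% (at most 0.40 × 0.023 = 0.009 SD).

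**The case against.** A common baseline slope is a legitimate specification, and with complete data the contrast is unbiased. That stands. It also stands that unequal dropout alone does no harm: the slope must change as well, and the documents give no slopes.

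Several stronger readings are tempting, and the documents do not support them.

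- A reader might infer from section 3.3.8.1.2 that controls will be disappointed and leave. That section gives limiting disappointment as a purpose of the psychoactive control; it does not predict disappointment.
- A reader might infer that section 3.3.12.1 expects unequal attrition. It plans a test for it and no more.
- A reader might take heavier-drinking controls leaving as the likely direction. The open-label psilocybin session offered after the double-blind period gives controls a reason to stay, and section 3.3.8.1.3 makes completing that period a condition for those who declined the second session. No passage supports either direction.
- A reader might take the 8-10% overstatement as the expected size. It rests on an extreme selection rule and on dropout timing that partly cannot arise: under the TLFB schedule, visit dropout falls after month 1, 2 or 5, not month 3. With feasible timing and graded selection it shrinks to 0.5-2.3%.

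Phone visits (section 3.3.11) and retrospective TLFB recall may also limit missing data. Finally, section 3.3.12.3.2 may be a summary, and the separate SAP may already contain the interaction.

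These points limit the size of the problem. They do not supply the missing term, show that the slope is constant, or bound loss at weeks 24 and 36.

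**Conclusion.** The concern holds in conditional form and at low severity. As listed, the primary model imposes one weeks 1-4 PHDD slope on eight months.

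- **Precision.** No loss if the slope is constant; about 1-4% in variance of the 8-month contrast under moderate decline; about 20% in the steepest decline tried.
- **Bias.** It needs a changing slope together with baseline-related dropout that differs by arm. It is about 0.01-0.02 SD or less at about 6% dropout or with graded selection, and about 0.02-0.07 SD at 20% dropout with strong arm-dependent selection. The upper value is roughly half a standard error (0.066/0.124). There is none when dropout is equal in both arms.

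If the monthly PHDD SD were 20-30 points (assumed), the trial-sized runs correspond to about 0.1-0.5 points at 6% dropout (0.007 × 20 to 0.018 × 30) and 0.4-2.0 points at 20% (0.022 × 20 to 0.066 × 30).

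The slopes, SD, correlations and dropout behind these sizes are all assumptions. The documents establish the omitted term and the absence of a bound on later dropout; they do not establish that bias will occur.

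**What to change.** Prespecify a weeks 1-4 PHDD-by-assessment interaction in the primary MMRM, and the matching baseline-by-assessment term in the PDA and DPDD models. Leave the other terms as planned. If the separate SAP already has the interaction, align section 3.3.12.3.2 with it.

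The cost is one line of text and 7 fixed-effect parameters per model, with no new data. If the slope proves constant, the price in precision is negligible (contrast SD 0.1120 against 0.1119). Fixing the term in advance is also more credible than adding it after the attrition comparisons in section 3.3.12.1 have been seen.

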### 3.3.3.2 Pilot Study Results

Figure 3 illustrates available pilot results by individual through week 8. Participants were 6 men and 4 women, mean age 40.1 (S.D. 10.3), who were concerned about their drinking but not interested in available treatment. Participants had been alcohol dependent for a mean of 15.1 years (S.D. 11.5) and ranged in severity from mild to severe dependence with a mean of 5.0 dependence criteria (S.D. 1.2).

Participants have tolerated psilocybin well in the pilot study. Transient mild headaches have been common during the 24 hours following psilocybin administration, as reported by Johnson et al. [109]. There have been no persisting adverse events that were considered related to the study treatments. Figure 3a shows mean scores on the Mystical Experience Questionnaire (MEQ) total score for the 10 participants receiving 0.3 mg/kg in the first session and 5 participants receiving 0.4 mg/kg in the second session, as well as scores reported at similar doses in normal volunteers by Griffiths et al. [110]. On average, acute effects are lower in magnitude than those seen at comparable doses in normal volunteers. Intensity of effects varied markedly from patient to patient, with MEQ scores ranging from .02 to .77 in the first session, and Hallucinogen Rating Scale (HRS) intensity scores ranging from 0 to 3.5. The mean score for the 0.4 mg/kg dose appears to be lower than that at 0.3 mg/kg. This is probably because the four participants with the strongest response in the first session did not receive 0.4 mg/kg in the second session.

Results (n=9) for the month before and the two months after the first psilocybin session are shown in Figures 3b-3d. Participants showed modest change in drinking behavior during the first month of psychosocial treatment. However, drinking days and heavy drinking days decreased significantly during the month following the first psilocybin session. Changes in drinking were accompanied by modest significant increases in self-efficacy (AASE confidence scale) following the psilocybin session. Importantly, the magnitude of the effects reported during the first psilocybin session (at week 4) is strongly correlated with changes in craving and self-efficacy in the week following the session, and with changes in drinking in the month following the session. In addition, changes in craving and self-efficacy at week 5 are correlated with changes in drinking during weeks 5-8 relative to weeks 1-4.

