### 3.3.5 Randomization and Blinding

Randomization will be performed as close as possible to the first drug administration session (on the morning of the session if possible) in order to restrict the intent-to-treat sample to patients who actually receive study medication. The randomization will be stratified by site and will consist of balanced varied size blocks within strata to ensure relative equality of assignment across treatment groups. The block sizes will not be revealed to participating investigators and will be randomly selected from a small number of different block sizes to help reduce the likelihood of an investigator predicting the next treatment assignment. The study statistician will generate the randomization scheme for each site, and the study pharmacist will assign treatment sequentially according the sequence for each site.

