#### 3.3.6.1 Inclusion Criteria

Participants will be:

- 1) Males and females age 25-65 with SCID (DSM-IV) diagnosis of alcohol dependence who
- 2) Want to stop or decrease their drinking
- 3) Are not participating in any formal treatment for alcohol dependence (12-step meetings are not considered treatment)
- 4) Are able to provide voluntary informed consent
- 5) Have at least 4 heavy drinking days in the past 30 days
- 6) If female of childbearing potential, are willing to use approved form of contraception# from screening until after the psilocybin administration sessions
- 7) Have a family member or friend who can pick them up and stay with them overnight after the psilocybin administration sessions
- 8) Are able to provide adequate locator information.

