##### ***3.3.8.1.3 Dosing and Administration of Study Medications***

Setting. The psilocybin sessions will take place in outpatient facilities that are appropriate for hallucinogen administration sessions. To the extent possible, the room used for the session will be specially prepared for the sessions to provide a warm and home-like rather than a stark clinical quality because of the large influence that setting can have on the subjective effects of hallucinogens. Each site will have detailed SOPs in place for managing medical or psychiatric emergencies should any occur.

Safety Screening on the Day of Drug Administration Sessions. Participants will be required to attempt to remain abstinent during the week preceding the drug administration sessions. On the morning of the psilocybin session, participants must have a negative breathalyzer reading, drug screen must be negative for all non-prescribed tested drugs of abuse except for marijuana, CIWA-Ar score must be less than 8, and vital signs must be within normal limits (afebrile, blood pressure less than or equal to 140 systolic, 90 diastolic, resting pulse less than 100). Female participants of childbearing potential must also have a negative urine pregnancy test.

Dosing of Study Medications. Individualized doses of psilocybin will be prepared by the site pharmacist using an analytical balance. Medication will be placed in an opaque gelatin capsule prior to administration, with the balance of the capsule volume filled with microcrystalline cellulose.

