### 3.3.10 Measures

Measures are listed in Table 1 below, organized by domain.

Table 1. Assessment Schedule		Scr.	BL	W04	W05	W08	W09	W12	W24	W36	W38	W39	W42	W54
Medical evaluation	History and physical, liver function tests, complete blood count, Chem 7, U/A, serum pregnancy test, height and weight, medical history intake form	550'												
	ECG		5'							5'				
	Concomitant meds, menstrual calendar		5'	5'	5'	5'	5'	5'	5'	5'	5'	5'	5'	5'
	Urine pregnancy test				5'		5'				5'			
Psychiatric and SUD assessment	Structured Clinical Interview for DSM-IV (SCID), Family History Questionnaire, Folstein MMSE	75'												
Other baseline characteristics	Attentional Resource Allocation Scale, Treatment Goal Form, Demographics Form, Locator Form			15'										
Withdrawal	CIWA-Ar	5'		5'		5'					5'			
Substance use and consequences	Time-line Follow-back, BAC	30'	10'	10'		10'		10'	10'	10'	10'		10'	10'
	Hair/ Nail sample for ethyl glucuronide									5'				
	Urine Drug Screen	5'		5'		5'		5'	5'	5'	5'		5'	5'
	Short Inventory of Problems (past 3 months)		5'					5'	5'	5'				5'
Acute Hallucinogen Effects	5D-ASC, HRS, SCQ, Monitor Rating Scale, Mysticism scale, guesses of medication received, MUSE questionnaire			30'		30'					30'			
Persisting Effects	Mysticism Scale (lifetime), Spiritual Transcendence Scale, Persisting Effects Questionnaire (follow-up)		90'							90'				90'

	only), BMMRS, NEO-PI-3, Schwartz Value Survey													
Motivation	Readiness rulers		5'	5'	5'	5'	5'	5'	5'	5'	5'	5'	5'	
Self-efficacy	Alcohol Abstinence Self-efficacy Scale		10'	10'	10'	10'	10'	10'	10'	10'	10'	10'	10'	
Craving	Penn Alcohol Craving Scale		5'	5'	5'	5'	5'	5'	5'	5'	5'	5'	5'	
Self-Compassion	Self-Compassion Scale (Short Form)		5	5	5	5	5	5	5	5	5	5	5	
Mood/ Anxiety	Ham-D, Ham-A		20'	20'	20'	20'	20'	20'	20'	20'	20'	20'	20'	
	Adverse Events Case Report Form			5'	5'	5'	5'	5'	5'	5'	5'	5'	5'	
Safety	Vital Signs and weight	5'	5'	5'	5'	5'	5'	5"	5'	5'	5'	5'	5'	
	Visual Analog Scales for abuse potential							5'	5'	5'			5'	
Tx satisfact.	Visual Analog Scales							5'					5'	
Assessment Length		185'	175'	110'	55'	110'	55'	85'	85'	170'	110'	55'	75'	170'

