### 3.3.10.4 Substance Use

#### 3.3.10.4.1 Self-report

The Time-line Follow-back (TLFB) [124, 125] procedure will be used to assess drug use behavior at baseline and follow-up visits. The TLFB is a semi-structured interview that provides estimates of the daily quantity, frequency, and pattern of drug use during a specified time period. It uses a calendar prompt and number of other memory aids (e.g., holidays, payday, and other personally relevant dates) to facilitate accurate recall of drug use during the target period. The TLFB has shown adequate to excellent reliability and validity over a wide range of research and clinical contexts [100, 126, 127]. It is estimated that the

TLFB assessment will take 10-30 minutes to complete, depending on the length of the assessment period and the patterns of alcohol and drug use. Non-study treatment and 12-step attendance will also be recorded on the TLFB form.

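### Optional gain: the primary MMRM's only drinking covariate is weeks 1-4 PHDD; adding the pre-treatment PHDD already collected could improve precision for one degree of freedom

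*Combined protocol and SAP*

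**What the plan says.** Section 3.3.12.3.2 (Aim 2, Method) models eight monthly PHDD values from week 5 to week 36. The fixed effects are treatment, assessment and site, with treatment-by-assessment and site-by-treatment interactions. The one drinking covariate is "a fixed covariate (week 1-4 PHDD"). The site terms are conditional: "Site and the site-by-treatment interaction will be removed from the final model if not significant at the" 0.05 level. PDA and DPDD are to be analysed in a similar way.

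Other sections bear on the covariate:

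- **Randomization (3.3.5):** "Randomization will be performed as close as possible to the first drug administration session", which is at week 4. Weeks 1-4 therefore precede randomization.
- **Treatment timing (Figure 2):** therapy sessions start at week 0 and run to week 12, and the next is at week 37.
- **Pre-session rule (3.3.8.1.3):** "Participants will be required to attempt to remain abstinent during the week preceding the drug administration sessions".
- **Drinking data (Table 1, 3.3.10):** the row "Time-line Follow-back, BAC" starts with entries at screening, baseline and week 4. Section 3.3.10.4.1 agrees that the "procedure will be used to assess drug use behavior at baseline and follow-up visits".
- **Eligibility (3.3.6.1):** participants must "Have at least 4 heavy drinking days in the past 30 days".

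Section 3.3.12.1 uses baseline drinking to compare groups and to study attrition and self-selection, not as a term in the primary model.

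**The concern.** Weeks 1-4 PHDD mixes a person's usual drinking with early response to therapy and with compliance with the abstinence request. That request covers about 7 of the 28 days, a quarter of the window. Most of the outcome period is different: six of the eight monthly outcomes (weeks 13-36) fall when no therapy is scheduled. A person's untreated drinking level could help predict those months beyond what weeks 1-4 PHDD already says.

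If so, prognostic variance that could be removed stays in the error term. The same error variance is used at the end of Stage 2 (section 3.3.13), where it is estimated from the primary model and informs the final sample size. What is at stake is efficiency. The validity of the treatment comparison is not in question.

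**Working it through.** **1. Inputs from the documents.** Section 3.3.12.7 gives N = 180 with 5% attrition, so 180 × 0.95 = 171; f² = 0.065; two-sided alpha 0.05; four predictors; power 0.80. No section gives a value for the error SD or for any correlation between pre-treatment, weeks 1-4 and outcome PHDD.

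**2. The plan's own figure.** With a noncentral F, noncentrality f² × N = 0.065 × 171 = 11.1 and 171 − 4 − 1 = 166 denominator degrees of freedom, power depends on how many of the four predictors are tested:

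| Predictors tested | Power |
|---|---|
| 4 jointly | 0.754 |
| 3 | 0.798 |
| 1 (treatment alone) | 0.912 |

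The stated 0.80 is reproduced when three are tested. The section does not say which reading was meant, so step 3 starts from the nominal 80% and step 5 repeats the sum from 0.912.

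**3. Effect of a second covariate.** Let r be the partial correlation of pre-treatment PHDD with the outcome, given weeks 1-4 PHDD. Error variance is multiplied by 1 − r². For a two-sided 5% test with 80% power the standardized effect is 1.96 + 0.8416 = 2.8016, so

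power = Φ(2.8016 / √(1 − r²) − 1.96), and equivalent N = 171 / (1 − r²).

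| Assumed r | Fall in error variance | Power | Equivalent N |
|---|---|---|---|
| 0 | 0% | 80.0% | 171 |
| 0.1 | 1% | 80.4% | 173 |
| 0.2 | 4% | 81.6% | 178 |
| 0.3 | 9% | 83.6% | 188 |

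For r = 0.2: 2.8016 / √0.96 = 2.859; 2.859 − 1.96 = 0.899; Φ(0.899) = 0.816.

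**4. Which values of r are plausible?** Let B be weeks 1-4 PHDD, S pre-treatment PHDD and Y mean outcome PHDD. With both covariates,

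R² = (r_BY² + r_SY² − 2 r_BY r_SY r_SB) / (1 − r_SB²).

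All the correlations below are assumptions.

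- S acts only through B (r_SY = r_BY × r_SB): no reduction, and power stays at 0.80.
- S somewhat weaker than B (r_SY = 0.8 r_BY), with r_BY 0.5-0.6 and r_SB 0.5-0.7: reduction 0.7-6.8%, power 0.803-0.827.
- S as prognostic as B (r_SY = r_BY), same ranges: reduction 5.9-18.8%, power 0.823-0.875.

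Example from the second case, with r_BY = 0.6, r_SB = 0.5 and r_SY = 0.48: R² = (0.36 + 0.2304 − 0.288) / 0.75 = 0.4032. Residual variance falls from 0.640 to 0.597, a 6.8% reduction.

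**5. Starting from the single-degree-of-freedom reading.** If 0.912 is the right base, r = 0.1, 0.2 or 0.3 gives 0.915, 0.923 or 0.935.

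**6. Cost.** One further predictor with no prognostic value moves power on the one-degree-of-freedom test from 0.80000 to 0.79997.

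**The case against.** The strongest reply is that the plan contains no mistake here. Weeks 1-4 PHDD precedes randomization, is the drinking measure closest to the outcome period, and reflects drinking under the background therapy on which the drug effect is tested. It may predict treated drinking better than an untreated rate does. All of that stands.

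The gain may also be small or nil. The pilot report says "Participants showed modest change in drinking behavior during the first month of psychosocial treatment", which suggests that the two measures could overlap heavily, and the entry criterion cuts off pre-treatment PHDD below about 13% (4/30). Both points carry some weight, but neither settles the matter. The pilot statement is a group summary in nine people and says little about differences between persons, and the criterion leaves the upper range open. The abstinence request points the other way.

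A reader might infer that adjusting for weeks 1-4 PHDD alone biases the result, or that the second covariate is bound to add precision. The documents support neither. Randomization comes after both measurements, so either adjustment set leaves the comparison valid. No correlation is reported, and a partial correlation of zero is possible. Nor is weeks 1-4 PHDD the model's only adjustment, since site terms are included when significant.

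Two practical objections also hold. The screening TLFB look-back is not stated. In addition, section 3.3.12 refers to a SAP for full detail; no separate SAP text was available for this check, so a further covariate listed there cannot be excluded.

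**Conclusion.** This is a free improvement, and a minor one. As section 3.3.12.3.2 stands, pre-treatment drinking is left out of the primary model although its collection is already scheduled. Adding it cannot bias the treatment contrast and costs one degree of freedom.

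The gain runs from nothing to 3.6 percentage points of power on a nominal 80% for an assumed partial correlation of 0 to 0.3, or at most 2.3 points if the base is 0.912. It would be larger only if pre-treatment PHDD were about as prognostic as weeks 1-4 PHDD, which the documents give no means of checking. No conclusion of the trial can be shown to depend on it.

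**What to change.** Before unblinding, and preferably before the Stage 2 check of error variance, amend section 3.3.12.3.2 and the SAP as follows:

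- Add pre-treatment PHDD as a second fixed continuous covariate beside weeks 1-4 PHDD, and keep it whatever its p-value.
- Define its window. The 30 days already used for eligibility is one natural choice. State the TLFB look-back to match, and whether the days are counted back from the screening or the baseline visit. Screening can take place up to four weeks before treatment starts, so the two differ.
- Use the analogous pre-treatment value in the PDA and DPDD models.
- If a separate SAP already lists such a covariate, align the two texts.

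The cost is a few lines of wording and one degree of freedom per model. No new visit, form or data collection is needed.

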### 3.3.2 Primary Outcome

The primary outcome for the study, used to test hypothesis 2, is percent heavy drinking days as assessed by the Time-line Follow-back [100], during the 32 weeks following the first drug administration session. Secondary drinking outcomes will include percent days abstinent, drinks per drinking day, days to first drinking day, days to first heavy drinking day, and consequences of drinking (from the Short Inventory of Problems [101]).

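### The last two monthly windows of the primary outcome share week 32, so eight windows total 33 weeks for a 32-week outcome

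*Combined protocol and SAP*

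**What the plan says.** The method for Aim 2 (section 3.3.12.3.2) fits a mixed model for repeated measures to "monthly values of PHDD (weeks 5-8, 9-12, 13-16, 17-20, 21-24, 25-28, 29-32, 32-36) as the dependent measure". The last three windows in that list read "25-28, 29-32, 32-36". The baseline adjustment is "a fixed covariate (week 1-4 PHDD"), a four-week window.

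The outcome itself is defined one subsection earlier, in 3.3.12.3.1, as "percent heavy drinking days during weeks 5-36 (the 32 weeks following the first drug administration session"). Section 3.3.2 gives the same length: "during the 32 weeks following the first drug administration session". The power section (3.3.12.7) speaks of "percent heavy drinking days in months 1-8 post pharmacologic treatment (Aim 2"), that is, eight months.

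Section 3.3.12 refers to the SAP for the full description of the analyses. The combined document contains no second list of windows that would confirm or override the one in 3.3.12.3.2.

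**The concern.** Eight monthly windows for a 32-week outcome should be eight blocks of four weeks. The printed list follows that pattern at every boundary (8/9, 12/13, 16/17, 20/21, 24/25, 28/29) except the last, where one window ends at week 32 and the next begins at week 32.

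The list is what a programmer would use to build the primary dependent variable. Followed literally, it puts the same drinking days into two of a participant's repeated measures and gives a different weighting of weeks from the outcome in 3.3.12.3.1. Corrected silently, the analysis departs from the written plan. Either way, the derivation of the primary endpoint rests on an undocumented choice.

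The same list carries over to percent days abstinent and drinks per drinking day, which 3.3.12.3.2 says are analysed in the same way. Aims 3 and 4 also take their drinking outcomes from Aim 2, although the Aim 4 method uses PHDD only at weeks 8 and 12 and so does not reach the last window.

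**Working it through.** **Inputs.** Windows as printed in 3.3.12.3.2: 5-8, 9-12, 13-16, 17-20, 21-24, 25-28, 29-32, 32-36. Outcome period from 3.3.12.3.1: weeks 5-36. Number of months from 3.3.12.7: 8.

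**The plan's own figure.** Counting weeks inclusively (end − start + 1), the outcome period is 36 − 5 + 1 = 32 weeks, as stated. Eight four-week months also give 8 × 4 = 32.

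**The windows as printed.**

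| Window | Length (weeks) |
|---|---|
| 5-8, 9-12, 13-16, 17-20, 21-24, 25-28, 29-32 | 4 each, 7 × 4 = 28 |
| 32-36 | 36 − 32 + 1 = 5 |
| Total | 33 |

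The total of 33 does not match 32. A tally of weeks 5 to 36 shows 32 distinct weeks, none missing and none outside the period; week 32 is the only one counted twice.

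**Effect on the weighting.** The section does not state which contrast from the model is primary. Assume, for illustration, an equally weighted average of the eight monthly values with complete data.

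- Intended weight of each week: 1/32 = 0.03125.
- Weeks 5-31 as printed: (1/4)/8 = 0.03125, unchanged.
- Week 32 as printed: (1/4 + 1/5)/8 = 0.05625, a ratio of 0.05625/0.03125 = 1.8.
- Each of weeks 33-36 as printed: (1/5)/8 = 0.025, a ratio of 0.025/0.03125 = 0.8.
- Check: 27 × 0.03125 + 0.05625 + 4 × 0.025 = 1.

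The weight moved to week 32 is 0.05625 − 0.03125 = 0.025, or 2.5% of the total. Let D be the treatment difference in week 32 minus the average treatment difference over weeks 33-36. The eight-month average then shifts by 0.025 × D. The month-8 value alone is one fifth week 32 and four fifths weeks 33-36, so its treatment difference shifts by 0.2 × D.

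**Effect on the repeated measures.** Months 7 and 8 share week 32. If weekly values were independent with equal variance (an illustration only), the shared week alone would give them a correlation of (1/4 × 1/5)/√(1/4 × 1/5) = 0.05/√0.05 = 0.22.

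**With the last window read as 33-36.** The lengths are 4 in all eight windows, the total is 32, and each of weeks 5-36 is covered exactly once.

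**The case against.** The best defence is that this is a typing slip which the plan itself resolves. The values are called monthly, seven of the eight windows are contiguous four-week blocks, and both the stated 32 weeks and the eight months admit only 33-36 as the last window. No sensible programmer would be misled for long. This stands, and it is why the point is minor.

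Second, even taken literally the list does little harm. The union of the windows is exactly weeks 5-36. PHDD is a percentage, so a five-week denominator leaves the scale unchanged. The overlap is the same in both arms, so there is no evident route to bias between groups. This stands too.

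Third, the week weights hold only for an equally weighted average with complete data, which the protocol does not name as its estimand; with missing months a likelihood-based estimate does not reduce to such simple weights. That is correct, and the weights should be read as an illustration of scale.

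Fourth, the SAP may already list 33-36, in which case an analysis programmed from it is unaffected. That cannot be settled from the combined document, which has only the one list.

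None of these points makes the printed list right. They limit its importance. It remains the only written definition of the monthly dependent measure in the text, and it disagrees with the outcome definition one subsection earlier.

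**Conclusion.** The point holds. As printed, the eight windows total 33 weeks for a 32-week outcome, week 32 is counted twice and the last month is five weeks long. The arithmetic needs no assumption beyond inclusive week counts, which the first seven windows confirm.

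The consequence is small. Under the assumed equal-weight average with complete data, 2.5% of the total weight moves from weeks 33-36 to week 32, in both arms. No effect on type I error or power has been shown, and the sample size calculation does not use the windows. This is a correction worth making because of where the slip sits, in the definition of the primary dependent variable. It is not a flaw in the design of the primary analysis.

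**What to change.** In section 3.3.12.3.2, change the last window to weeks 33-36. All eight windows are then four weeks long, do not overlap, cover weeks 5-36 exactly once, and match the length of the weeks 1-4 baseline covariate.

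Check any window list in the SAP and in the derivation specifications for PHDD, percent days abstinent and drinks per drinking day, and align them. Because the point turns on one digit, confirm it against the signed protocol before issuing the correction.

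The cost is one number in the protocol, plus the same edit in the SAP if the slip is repeated there. Sample size, alpha, power, visits and data collection do not change.
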